**By NRS-11 Score:**

The subject is considered to be as responder if, each NRS11 symptoms change from baseline score at the end of the study treatment is at least 2 (i.e., NRS-11 symptoms CFB  $\geq -2$ ). only subjects with a score of the respective symptom of at least 5 at baseline will be used.

▪ **Treatment acceptance and ease of use assessed by Likert Scale**

Convert the responses of treatment acceptance into numeric score as follows and analyze the scores:

Acceptance response	Score
Not at all satisfied	1
Slightly satisfied	2
Neutral	3
Very satisfied	4
Extremely satisfied	5

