### **Symptoms of dyspepsia assessed by Numerical Rating Scale (NRS 11)**

- The Numerical Rating Scale is widely used for self-reporting of pain intensity in clinical practices. In this study, the participants will be provided with the NRS 11 scale to mark changes for symptoms of sensation of bloating, early satiety, postprandial fullness, upper abdominal pain or discomfort (epigastric pain, epigastric burning), anorexia (loss of appetite), heartburn, nausea and vomiting at baseline and after 4 and 8 weeks of treatment.
- NRS 11 will be used to assess responders' analysis for adequate/satisfactory relief.
- NRS 11 and drug intake will be captured in patient diary. Drug intake will be recorded by the subject on a daily basis, symptoms will be recorded by the subject over the last two weeks prior to the visits. In addition, the baseline NRS 11 scores will be captured on site.

SYMPTOMS	SCALE										
	0	1	2	3	4	5	6	7	8	9	10
	No	Very Mild	Discomforting	Tolerable	Distressing	Very Distressing	Intense	Very Intense	Horrible	Unbearable	Unpeakable
Bloating sensation											
Early satiety											
Postprandial fullness											
Upper abdominal pain or discomfort (epigastric pain, epigastric burning)											
Anorexia (loss of appetite)											

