### Transformation for Standardized Score,

Convert the responses of QoL items into numeric scores as per step 1 and categorize the five domains as per step 2 defined above for transformation of raw score.

Step 3:

Calculate the score of each domain as follows:

Tension = Score of 1 + Score of 2; similarly for each domain.

Step 4:

Transform the domain scores as follows:

*Transformed Scale Score*

$$= 100 - \left[ \frac{(\text{Actual Raw Score} - \text{Minimum Possible Score})}{\text{Range}} \times 100 \right]$$

Where,

*Minimum Possible Score = 2*

*Range = (Maximum Possible Score – Minimum Possible Score) = (10 – 2) = 8*

Note:

Each item is scored on likert scale and converted into numeric scores as per step 1. Each domain is measured using 2 questions as per step 2.

Step 5:

overall SF-NDI total score is obtained by mean of 5 domain score as follows:

Overall QoL Transformed Score

=

Transformed scores for (Tension + Interference with daily activities + Eating/Drinking + knowledge/Control + Work/Study) ÷ 5

The following simulated example of patient's response and score calculation can be referred for better understanding of the scoring procedure:

Question No.	Response	Converted Response Into Numeric Score	Categorization of Domains	Score for each domain	Transformed Scale Score
1	QUITE A LOT	4	Tension	$4 + 3 = 7$	$\frac{(7 - 2)}{8} \times 100 = 62.5$
2	MODERATELY	3			
3	EXTREMELY	5	Interference with daily activities	$5 + 4 = 9$	$\frac{(9 - 2)}{8} \times 100 = 87.5$
4	QUITE A LOT	4			
5	MODERATELY	3	Eating/Drinking	$3 + 4 = 7$	$\frac{(7 - 2)}{8} \times 100 = 62.5$
6	QUITE A LOT	4			
7	FAIRLY OFTEN	3	knowledge/Control	$3 + 5 = 8$	$\frac{(8 - 2)}{8} \times 100 = 75.0$
8	ALWAYS	5			
9	QUITE A LOT	4	Work/Study	$4 + 3 = 7$	$\frac{(7 - 2)}{8} \times 100 = 62.5$
10	MODERATELY	3			

Overall QoL Transformed Score	$(62.5 + 87.5 + 62.5 + 75.0 + 62.5) \div 5 = 70.0$
-------------------------------	--

▪ **Symptoms of dyspepsia assessed by Numerical Rating Scale (NRS 11)**

Convert each NRS 11 responses into numeric score as follows:

Symptom response	Score
No	0
Very Mild	1
Discomforting	2
Tolerable	3
Distressing	4
Very distressing	5
Intense	6
Very Intense	7
Horrible	8
Unbearable	9
Unspeakable	10

Each symptom will be analyzed separately according to symptom score.

▪ **Responders for adequate/satisfactory relief as assessed**

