**By NRS-11 Score:**

The subject is considered to be as responder if, each NRS11 symptoms change from baseline score at the end of the study treatment is at least 2 (i.e., NRS-11 symptoms CFB  $\geq 2$ ). only subjects with a score of the respective symptom of at least 5 at baseline will be used.

Source: LXX00X.sas, <CRO>.Run DDMMYYYY HH:MM  
Abbott Protocol CCCC-xxx-yyyy

Page x/y

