**By NRS-11 Score:**

The subject is considered to be as responder if, each NRS11 symptoms change from baseline score at the end of the study treatment is at least 2 (i.e., NRS-11 symptoms CFB  $\geq -2$ ). only subjects with a score of the respective symptom of at least 5 at baseline will be used.

Source: LXX00X.sas, <CRO>.Run DDMMMYYYY HH:MM  
Abbott Protocol CCCC-xxx-yyyy

Page x/y

*Repeat similar table for* **10.1.2.2.5.3 Responder Analysis of Satisfactory Relief Assessed by LDQ and/or NRS 11 (by Age Group)**

*Repeat similar table for* **10.1.2.2.5.4 Responder Analysis of Satisfactory Relief Assessed by LDQ and/or NRS 11 (by Geographical Region)**

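### The NRS-11 responder cut-off is wrong as written (inequality reversed) and differs between SAP 5.3.2 and the overall table shell

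*SAP*

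**What the plan says.** The protocol synopsis lists a responder analysis of adequate or satisfactory relief, by LDQ and/or NRS-11, as a secondary endpoint. Protocol 8.1 adds that "NRS 11 will be used to assess responders' analysis for adequate/satisfactory relief". The NRS-11 scoring table in SAP 5.3.2 runs from 0 for no symptom to "Unspeakable 10", so a higher score is worse.

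The responder rule is printed in three places in the SAP:

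- SAP 5.3.2, By NRS-11 Score: the change from baseline at the end of study treatment "is at least 2 (i.e., NRS-11 symptoms CFB $\geq -2".
- Note 2 to the overall shell, Table 10.1.2.2.5.1: the same sentence, but with "i.e., NRS-11 symptoms CFB $\geq 2".
- Note 2 to the by-gender shell, Table 10.1.2.2.5.2: "i.e., NRS-11 symptoms CFB $\geq -2". The age-group and region tables are to repeat this shell.

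All three carry the same restriction: "only subjects with a score of the respective symptom of at least 5 at baseline will be used". SAP 4.2.2 classifies subjects symptom by symptom and compares the arms with a chi-square or Fisher's exact test. In the table list of SAP 9.3.1, only the overall responder table is marked for headline results. SAP section 7 does not mention the difference between the formulas.

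**The concern.** A responder here should be someone whose symptom got better. On a scale where higher is worse, improvement by at least 2 points is a change of −2 or lower. The body text has the number −2 but the inequality points the other way, so it sets a ceiling on improvement instead of a floor. The overall shell has lost the minus sign as well, or assumes a different order of subtraction. The headline table and its subgroup tables could therefore be programmed to different rules from the same SAP. At stake is a named secondary endpoint, reported for eight symptoms, overall and by gender, age group and country.

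**Working it through.** The plan gives no figure that depends on this cut-off, so there is nothing to reproduce. The check is an enumeration.

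**Inputs.** Baseline scores 5 to 10 (the SAP restriction) and end-of-treatment scores 0 to 10 give 6 × 11 = 66 possible pairs. Of these, 15 are worsening (5+4+3+2+1+0), 6 unchanged, 6 improved by 1, 6 improved by 2, and 33 improved by 3 or more (3+4+5+6+7+8).

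**Responders with CFB = post minus baseline:**

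| Rule | Worse (15) | Same (6) | Improved by 1 (6) | Improved by 2 (6) | Improved by ≥ 3 (33) |
|---|---|---|---|---|---|
| CFB ≥ −2 (5.3.2, by-gender shell) | 15 | 6 | 6 | 6 | 0 |
| CFB ≥ 2 (overall shell) | 10 | 0 | 0 | 0 | 0 |
| CFB ≤ −2 (decrease of at least 2) | 0 | 0 | 0 | 6 | 33 |

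Measured against a decrease of at least 2, the text rule is right only for an exact 2-point improvement. It misclassifies 15 + 6 + 6 + 33 = 60 of 66 pairs. The overall-shell rule misclassifies 10 + 6 + 33 = 49 of 66. The mock subject in Listing 12.2.6.4.1 (9 at baseline, 3 at week 8, change −6) fails under both printed rules.

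**Responders with CFB = baseline minus post:**

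| Rule | Worse (15) | Same (6) | Improved by 1 (6) | Improved by 2 (6) | Improved by ≥ 3 (33) |
|---|---|---|---|---|---|
| CFB ≥ −2 | 9 | 6 | 6 | 6 | 33 |
| CFB ≥ 2 | 0 | 0 | 0 | 6 | 33 |

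The overall shell is now correct. The text rule still admits 9 + 6 + 6 = 21 pairs that are not an improvement of 2: worsening by 1 or 2, no change, and improvement by 1.

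**Illustration of rates.** The pair counts are not probabilities, and the documents give no NRS-11 means or SDs. I assume a normal change (post minus baseline) rounded to whole points, with means −2, −3 and −4 and SD 2 to 3, ignoring the ends of the scale. For mean −3 and SD 2.5:

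- Intended rule: P(CFB ≤ −2) = Φ((−1.5 + 3)/2.5) = Φ(0.6) = 0.726
- Text rule: P(CFB ≥ −2) = 1 − Φ((−2.5 + 3)/2.5) = 1 − Φ(0.2) = 0.421
- Overall-shell rule: P(CFB ≥ 2) = 1 − Φ((1.5 + 3)/2.5) = 1 − Φ(1.8) = 0.036
- Misclassified by the text rule: 1 − P(CFB = −2) = 1 − (0.726 − 0.579) = 0.853

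| Mean change | Intended rule, SD 2 / 2.5 / 3 | Text rule, SD 2 / 2.5 / 3 | Overall-shell rule, SD 2 / 2.5 / 3 |
|---|---|---|---|
| −2 | 60 / 58 / 57% | 60 / 58 / 57% | 4 / 8 / 12% |
| −3 | 77 / 73 / 69% | 40 / 42 / 43% | 1 / 4 / 7% |
| −4 | 89 / 84 / 80% | 23 / 27 / 31% | 0 / 1 / 3% |

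At mean −2 the text rule gives the right rate by symmetry, although it labels mostly the wrong subjects. If one arm has mean −3 and the other −4, the arm with more relief has the higher rate under the intended rule and the lower rate under both printed rules.

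**The case against.** Several points on the other side are fair.

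- **Order of subtraction.** The SAP does not write it out for NRS-11 and refers some definitions, baseline among them, to Module 2, which is not available here. With baseline minus post the overall shell is exactly right. This stands. A reader might infer that all the printed rules are wrong whatever the convention, and that goes too far. The body text and by-gender note, however, are wrong under either order.
- **Possible extraction fault.** The overall and by-gender notes differ by one minus sign in machine-read text, so a minus lost in conversion cannot be excluded. If so, the inconsistency disappears, but all three places then carry the reversed inequality.
- **Recoverable intent.** The words say at least 2, under a heading about relief, and the SAP gives no sample code for responders. A careful programmer may well implement a 2-point decrease. A reader might infer that the reported results will be inverted. The documents do not show that: the harm arises only if the printed formula is followed. Still, the words give no direction and the formula is the only operational rule.
- **Reach.** A reader might infer a threat to the trial's main conclusion. SAP 4.2.1 rests success on the week 8 LDQ comparison alone, and protocol 10.2 treats the secondary variables as mainly descriptive. Of the responder tables, only the overall one is a headline output.

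It is also tempting to settle here how rescue users and missing values count in the responder analysis. That is a separate question. Protocol 10.1 takes the last non-missing on-treatment value as the efficacy endpoint, while protocol 10.2 and SAP section 4 (Other analysis) have their own provisions on the impact of rescue medication. Nothing about the inequality decides it.

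**Conclusion.** The point holds and should be corrected. In SAP 5.3.2 and the by-gender note the inequality is reversed, and under either subtraction order the rule counts unchanged subjects and some or all worsening subjects as responders. The overall note, as printed, states a different rule, which is correct only with baseline minus post.

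With post minus baseline, which the term change from baseline and the −2 both suggest, literal use misclassifies 60 of 66 score pairs under the text rule. Under the illustrative assumptions, about 80% to 89% of subjects are misclassified, and the better arm can look worse. The percentages rest on assumed means and SDs; the enumeration and the direction of the error do not. The consequence is limited to the secondary NRS-11 responder tables and their subgroup versions. The LDQ primary analysis, the LDQ responder rule (overall score below 9) and the sample size do not depend on this rule.

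**What to change.** Replace the rule with one identical sentence in SAP 5.3.2 and in Note 2 of Tables 10.1.2.2.5.1 and 10.1.2.2.5.2:

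> Responder for a symptom = decrease from baseline of at least 2 points at the end of study treatment (end-of-treatment score minus baseline ≤ −2), among subjects with a baseline score of at least 5 for that symptom.

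This states both the direction and the order of subtraction. It keeps the SAP's end-of-treatment timing and baseline restriction. The age-group and region tables inherit it from the by-gender shell. Make the edit before database lock and record it in SAP section 7, so that the definition remains pre-specified. The cost is wording in three places, with no change to data collection, sample size or table layout.

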#### 5.4 Non-standard Safety Data

Not Applicable

#### 5.5 Drug Accountability and Exposure

##### 5.5.1 Drug Accountability

Drug accountability will be defined as the number of tablets that were actually taken relative to the number of tablets that should have been taken for the duration of actual treatment exposure.

The overall compliance assessed by tablets count will be calculated as follows:

$$\text{Treatment Compliance (\%)} = \left[ \frac{\text{N of capsules/tablets dispensed} - \text{N of capsules/tablets returned}}{(\text{LDA} * \text{N of capsules/tablets prescriber per day})} \right] \times 100$$

Where,

N of tablets dispensed = N of tablets dispensed at baseline + N of tablets dispensed at visit 3 (week 4)

N of tablets returned = N of tablets returned at visit 3 (week 4) + N of tablets returned at visit 4 (week 8)

LDA = Day number of the last day of drug administration

The calculated compliance will be categorized as:

Too Low: Compliance of drug < 80%

Adequate:  $80\% \leq \text{Compliance of drug} \leq 120\%$

Too High: Compliance of drug > 120%

Overall compliance be summarized descriptively, and the compliance categories will be summarized using frequency count (n) and percentages (%) by treatment group.

### **5.5.2 Exposure**

Exposure to treatment in duration will be summarized descriptively by treatment groups for safety subject sample.

Duration of treatment exposure will be calculated as follows:

Exposure = Date of last drug administration – Date of first drug administration + 1

## 6. FURTHER SPECIFICATIONS TO THE STANDARD ANALYSES IN MODULE 2

### 6.1 Trial Design [2]

#### 6.1.1 Trial Periods

The combination of trial arms and trial periods for the current trial is presented in the following diagram:

	Screening Period	Treatment Period	Follow-up Periods
Test Arm	2 weeks	8 weeks	1 week
Active Control Arm	2 weeks	8 weeks	1 week

#### 6.1.2 Trial Elements

The start time of each intervention will be expressed relative to <<the first administration of investigational study drug/medication/start of the infusion>> closest to that intervention.

The Trial Elements are presented in the following diagram:

Trial Element	Description of Element	Rule for Start of Element	Rule for End of Element	Planned Duration of Element
Screen	Screening Period	Date of Informed Consent	First dose of study treatment	NA
Itopride Hydrochloride 150 mg (administered once daily)	Treatment Period; Test Arm	First dose of Test Arm	Last dose of Test Arm	8 weeks or less
Itopride Hydrochloride 50 mg (administered TID)	Treatment Period: Active Control Arm	First dose of Active Control Arm	Last dose of Active Control Arm	8 weeks or less
Follow up	Follow up period	Last dose of study treatment	Investigator's phone call after end of treatment visit	7 days or less

### 6.1.3 Trial Arms

The trial arms for this study are made up of the following trial elements:

Trial Arm	Elements			
	Screen	Itopride Hydrochloride 150 mg (administered once daily)	Itopride Hydrochloride 50 mg (administered TID)	Follow-up
Test Arm	Y	Y	N	Y
Active Control Arm	Y	N	Y	Y

### 6.1.4 Visits and related definitions

Tests and examinations that were scheduled in the protocol will be related to the general time axis of the trial by relating the visit date on which a test or examination is performed to the start date of the trial element that describes the first administration of investigational study drug closest in time to the visit date of that test or examination (Reference Start Date/ Time).

Test / Examination	Visit name	Visit Label	Visit Number	Reference Start Date/Time	Relative Day Number
Informed Consent	Screening	Screening	1	Date of first dose of study treatment	Day -1
Inclusion/Exclusion	Screening	Screening	1	Date of first dose of study treatment	Day -1
Inclusion/Exclusion	Baseline	Treatment Period	2	Date of first dose of study treatment	Day 1
Demographic Data	Screening	Screening	1	Date of first dose of study treatment	Day -1
Medical History	Screening	Screening	1	Date of first dose of study treatment	Day -1
Randomization	Baseline	Treatment	2	Date of first dose of study	Day 1

		Period		treatment	
Physical Examination	Screening	Screening	1	Date of first dose of study treatment	Day -1
Physical Examination	Baseline	Treatment Period	2	Date of first dose of study treatment	Day 1
Physical Examination	Treatment Period	Treatment Period	3	Date of first dose of study treatment	Day 29
Physical Examination	End of Treatment	End of Treatment	4	Date of first dose of study treatment	Day 57
Height	Screening	Screening	1	Date of first dose of study treatment	Day -1
BMI, Weight	Screening	Screening	1	Date of first dose of study treatment	Day -1
BMI, Weight	Baseline	Treatment Period	2	Date of first dose of study treatment	Day 1
BMI, Weight	Treatment Period	Treatment Period	3	Date of first dose of study treatment	Day 29
BMI, Weight	End of Treatment	End of Treatment	4	Date of first dose of study treatment	Day 57
Vital signs	Screening	Screening	1	Date of first dose of study treatment	Day -1
Vital signs	Baseline	Treatment Period	2	Date of first dose of study treatment	Day 1
Vital signs	Treatment Period	Treatment Period	3	Date of first dose of study treatment	Day 29

Vital signs	End of Treatment	End of Treatment	4	Date of first dose of study treatment	Day 57
Hematology	Screening	Screening	1	Date of first dose of study treatment	Day -1
Hematology	End of Treatment	End of Treatment	4	Date of first dose of study treatment	Day 57
Biochemistry	Screening	Screening	1	Date of first dose of study treatment	Day -1
Biochemistry	End of Treatment	End of Treatment	4	Date of first dose of study treatment	Day 57
Pregnancy test	Screening	Screening	1	Date of first dose of study treatment	Day -1
Test report for H. pylori 	Screening	Screening	1	Date of first dose of study treatment	Day -1
Upper GI Ultrasound	Screening	Screening	1	Date of first dose of study treatment	Day -1
Endoscopy	Screening	Screening	1	Date of first dose of study treatment	Day -1
ECG	Screening	Screening	1	Date of first dose of study treatment	Day -1
Leeds Dyspepsia Questionnaire (LDQ)	Screening	Screening	1	Date of first dose of study treatment	Day -1
Leeds Dyspepsia Questionnaire (LDQ)	Treatment Period	Treatment Period	3	Date of first dose of study treatment	Day 29
Leeds Dyspepsia Questionnaire (LDQ)	End of Treatment	End of Treatment	4	Date of first dose of study treatment	Day 57

				treatment	
SF-NDI questionnaire	Baseline	Treatment Period	2	Date of first dose of study treatment	Day 1
SF-NDI questionnaire	End of Treatment	End of Treatment	4	Date of first dose of study treatment	Day 57
NRS 11 (Onsite)	Baseline	Treatment Period	2	Date of first dose of study treatment	Day 1
NRS 11 (patient diary)	Baseline	Treatment Period	2	Date of first dose of study treatment	Day 1
NRS 11 (patient diary)	Treatment Period	Treatment Period	3	Date of first dose of study treatment	Day 29
Adverse Event	Screening	Screening	1	Date of first dose of study treatment	Day -1
Adverse Event	Baseline	Treatment Period	2	Date of first dose of study treatment	Day 1
Adverse Event	Treatment Period	Treatment Period	3	Date of first dose of study treatment	Day 29
Adverse Event	End of Treatment	End of Treatment	4	Date of first dose of study treatment	Day 57
Adverse Event	Follow up	Follow up	TC	Date of first dose of study treatment	Day 64
Concomitant Medication	Screening	Screening	1	Date of first dose of study treatment	Day -1
Concomitant Medication	Baseline	Treatment Period	2	Date of first dose of study treatment	Day 1

Concomitant Medication	Treatment Period	Treatment Period	3	Date of first dose of study treatment	Day 29
Concomitant Medication	End of Treatment	End of Treatment	4	Date of first dose of study treatment	Day 57
Concomitant Medication	Follow up	Follow up	TC	Date of first dose of study treatment	Day 64
Drug Return and Accountability	Treatment Period	Treatment Period	3	Date of first dose of study treatment	Day 29
Drug Return and Accountability	End of Treatment	End of Treatment	4	Date of first dose of study treatment	Day 57
Treatment acceptance and ease of use	End of Treatment	End of Treatment	4	Date of first dose of study treatment	Day 57

## 6.2 Further Specifications to the Standard Tables in Module 2

Not Applicable

## 6.3 Other Further Specifications

Not Applicable

## 7. CHANGES TO PLANNED ANALYSES

### 7.1 Changes to the Analysis Laid Down in the Protocol

Change in	Study Protocol	Statistical Analysis Plan
Subject sample	All subjects randomized to treatment sample has been used	Changed to All subjects allocated to treatment subject sample

### 7.2 Changes from previous SAP Version

Sr. No.	Changes
1	Added General Considerations for the Analysis section
2	Included sample SAS code for Missing Values Imputation and for MMRM Model.
3	Summarized all 15 symptoms of SF-NDI as a score in addition to individual symptom's summaries
4	QoL domains are now summarized based on both raw scores and transformed scores; initially, only raw scores were provided. Derivation also added for transformed scores.
5	Updated AE table summarizing adverse events with incidence $\geq 3\%$ instead of incidence $\geq 5\%$
6	Elaborated the Safety Analysis section and added other analysis section specifying baseline tables, summaries, and listings.
7	Defined markedly abnormal ranges for non-standard variables of Hematology and Biochemistry.

## 9. APPENDICES

### 9.1 Study Flowchart

All study assessments will be conducted as indicated in the below Table, which displays the frequency and timing of all measurements.

**Table : Study Assessments**

[figure not shown]
Periods	Screening period	Treatment period			Follow up
Visits (V)	V1	V2	V3	V4 (ET/ED)	TC
Week			W4	W8	
Day	Day -1	Day 1	Day 29	Day 57	Day 64
Visit window	-14 to -1 days		±1 day	±1 day	+1 day
Informed Consent	X				
Demographic data	X				
Medical history	X				
Inclusion/Exclusion criteria	X	X			
Physical examination	X	X	X	X	
Weight, Height (screening only), BMI 	X	X	X	X	
Vital signs	X	X	X	X	
Hematology	X			X	
Biochemistry (including RBS, Serum prolactin (fasting), Serum lipase  )	X			X	
Pregnancy test 	X				
Test report for H. pylori 	X				
Upper GI Ultrasound	X				
Endoscopy 	X				
ECG	X				
Randomization		X			
Leeds Dyspepsia Questionnaire (LDQ)	X		X	X	
Short From Nepean Dyspepsia Index (SF-NDI) questionnaire		X		X	
NRS 11 onsite (baseline only)		X			
Patient diary distribution		X	X		
NRS 11 recorded in patient diary 		X	X		
Dispense Study drug		X	X		
Drug intake recorded in patient diary 		X	X		
Diary return			X	X	

Study drug return			X	X	
Study drug accountability and adherence assessment			X	X	
Adverse events	X	X	X	X	X
Concomitant medications	X	X	X	X	X
Treatment acceptance and ease of use assessment using Likert scale				X	

ET – End of treatment, ED – Early discontinuation, TC – Telephone contact, D – day, V – Visit

1. For women of child-bearing potential (including those without history of surgical sterilization and women with <2 years post-menopause)
2. H. pylori test report in medical history within 3 months before randomization, otherwise to be performed during screening.
3. Endoscopy in medical history within 6 months before randomization, otherwise to be performed during screening.
4. Symptoms will be recorded by the subject over the last 2 weeks prior to the next visit.
5. Will be calculated during analysis, not by investigator.
6. Will be recorded daily.
7. Serum Lipase at V1 (baseline) only.

